DirecNet completed a randomized, controlled trial of the GlucoWatch Biographer (GWB), with HbA_{1c} and "blinded" use of the Medtronic CGMS as primary outcomes.⁵⁶ A sample of 200 highly motivated, compliant T1DM patients with mean baseline HbA_{1c} of 7.9% was randomized to SMBG alone or augmented with GWB use for 6 months. The study showed that the GWB did not affect glycemic control, hypoglycemia, quality of life, or adherence. GWB use declined steadily and 26% of patients stopped using it. Skin problems, gaps in data, inaccuracy, and calibration failures limited benefit from the device.

DirecNet also evaluated the accuracy of the Freestyle Navigator⁶² and completed pilot studies of its clinical utility among 30 youths with T1DM on insulin pumps² and 27 youths on multiple daily injections.³⁻⁴ Complete data are available for 13 weeks' use of the Navigator for 51 of the 57 children who enrolled. A total of 9 patients stopped using the Navigator within 13 weeks, 2 on insulin pumps and 7 on MDI regimens. Mean HbA_{1c} declined significantly for pump patients ($p < .01$) and for MDI patients ($p < .04$) over 13 weeks, with larger decreases among patients with higher baseline HbA_{1c} on either regimen. Further slight decreases in HbA_{1c} have been observed among the patients who have continued using the Navigator for up to 18 months. *There was no change in the frequency of severe hypoglycemia relative to the 6 months prior to enrollment for either sub-sample, showing that reduction in HbA_{1c} was not accompanied by increased risk of severe hypoglycemia. Scores on the Continuous Glucose Monitor Satisfaction Scale were uniformly positive for both pump and MDI participants.* Among pump patients, the added Navigator burden did not adversely affect quality of life for parents or children. Youths on MDI regimens, but not their parents, reported significantly improved scores on the PedsQL Diabetes Module¹³⁶ after 13 weeks of CGS use. All of these results should be interpreted in context, since the enrolled children and parents were carefully selected and highly motivated and may not be representative of the broader clinical population.

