4.4. Behavior Therapy for Families of Diabetic Adolescents (1-R01-DK-43802). [name] was also PI on this NIH-funded multi-center trial that has completed its second funding cycle. During the first funding cycle, BFST yielded improved parent-adolescent relationships and reduced family conflict about diabetes, but these changes did not yield corresponding improvements in treatment adherence or glycemic control.¹¹⁻¹³ In the second funding cycle, the BFST intervention was revised to enhance its impact on diabetes outcomes. A sample of 104 adolescents with HbA_{1C} \geq 8.0% enrolled at Nemours Children's Clinic and at Washington University School of Medicine. Families were randomized to Standard Care alone or augmented by 6 months' treatment either in a multifamily educational support group or in Behavioral Family Systems Therapy. The revised intervention exerted substantially greater effects on adherence and glycemic control, particularly among youths with HbA_{1C} above 9.0%. The revised BFST-D yielded durable improvements in adherence and glycemic control clearly relative to the Standard Care group and more equivocally relative to the Educational Support group, and similar effects occurred on measures of directly observed family communication.¹⁴⁻¹⁶ This confirms [name] capacity to coordinate a multi-site intervention trial and the studies provided substantial experience with family problem solving and communication training interventions in T1DM. Many of the intervention educational materials and handouts developed for this work will be used in the planned trial.

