- Not enrolled in special education for mental retardation, autism or severe behavior disorders.
- Primary diabetes caregiver not diagnosed or in treatment for major depression, psychosis, bipolar disorder or substance use disorder within the 6 months prior to enrollment; Child not in an inpatient psychiatric unit or day treatment program during the 6 months prior to enrollment.
- Family has working telephone service.

The objective is to enroll 150 youths with T1DM with HbA_{1C} above target despite treatment with intensified T1DM regimens. *We limited enrollment to youths with $HbA_{1C} \geq 7.5\%$ and $\leq 10.0\%$ since they have much to gain in terms of improved glycemic control, reduction of health care costs and deferral of complications. Youths with $HbA_{1C} < 7.5\%$ have different goals for adding CGS to diabetes care, such as decreased severe hypoglycemia and glycemic variability rather than reduction in HbA_{1C} , while those with $HbA_{1C} > 10.0\%$ may be unable to use CGS safely.* Inclusion of two sub-samples with differing primary outcomes would create analytic problems that are avoided with a more homogeneous sample. The JDRF Artificial Pancreas Project will enroll a sub-sample of patients with $HbA_{1C} < 7.0\%$, while our study will make a unique contribution by focusing on adolescents with suboptimal glycemic control.

5.3. Stratified randomization *Youths entering the study must have been on a T1DM regimen for ≥ 6 months comprising either a "basal-bolus" multiple daily injection (MDI) or continuous subcutaneous insulin infusion (CSII; insulin pump) regimens using carbohydrate counting and insulin correction factors. To promote equality of the groups in HbA_{1C} , randomization will be stratified by two HbA_{1C} levels: $\leq 8.8\%$ and $> 8.8\%$. Separate*

randomization lists will be used for each center and HbA_{1c} stratum. After the baseline evaluation, adolescents within each stratum will be randomized with equal probability to the three groups (SC, CGS or CGS+BT) so that each center randomizes similar numbers into each group and so that the groups are similar in HbA_{1c}.

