Statistical analysis will begin with treatment of missing data, preliminary descriptive analysis and visual inspection of distributions.¹⁵⁵⁻¹⁵⁶ Appropriate transformations of variables will be used to restore normality if needed. Baseline values of the primary outcome and predictor variables will be compared to determine if there are significant pretreatment differences between the groups that require adjustments. Visual examination of scatter plots, histograms and other graphical summaries will be used to identify possible associations or treatment effects of interest. Where multiple statistical comparisons are planned, we will make appropriate multiplicity adjustments.¹⁵⁵⁻¹⁵⁸ Internal consistency will be calculated for each psychometric measure based on

data from this study and only those with $\alpha \geq .70$ will enter data analyses. Upon completion of these preparatory activities, we will apply Individual Growth Modeling¹⁶⁰⁻¹⁶¹ to test the hypotheses listed below (see Section 5.12 for details).

5.10. Hypotheses. The following hypotheses, corresponding to the three specific aims, will be tested:

Hypothesis 1: Adolescents in CGS+BT will show more improvement in glycemic control (HbA_{1C}, Kovatchev's measures of glycemic variability derived from SMBG and CGS data, and proportion of CGS values in the normal range) compared with those in SC and CGS over the 9-month Randomized Phase.

Hypothesis 2: Adolescents in CGS+BT will realize more improvement in diabetes-related behavioral outcomes (Diabetes Self-Management Profile; PedsQL Diabetes Module; Diabetes Responsibility and Conflict Scale; Hypoglycemia Fear Survey; Blood Glucose Monitoring Communication Questionnaire: Blood Glucose Monitoring System Rating Questionnaire) compared with those in SC and CGS and in scores on the CGM Satisfaction Scale (CGS vs CGS+BT only) over the 9-month randomization phase of the study.

Hypothesis 3a: Improvements in HbA_{1C} during the 9-month Randomized Phase will be moderated by adolescents' and parents' baseline status on the following measures: Socioeconomic status; Family composition; Adolescent age; Diabetes Problem Solving Interview, Parent-Adolescent Relationship Questionnaire; Diabetes Family Responsibility Questionnaire; Wiebe Parental Supportive Involvement Interview; and Diabetes Responsibility and Conflict Scale).

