To evaluate the treatment effects on the change of glycemic control over time, HbA_{1c} measured from baseline to end of study will be the outcome variable in the level-1 model. A participant without missing values will have a total of 5 measures of HbA_{1c}. The time interval between baseline and the measure of each HbA_{1c} in the unit of months will be the Time variable in the level-1 model. The shape of the HbA_{1c} trajectory will be determined statistically by comparing a linear model and a quadratic model using the AIC and BIC indices produced by SAS Proc Mixed. In level-2 models, X_i will be a dummy variable indicating treatment groups. For example, to evaluate the treatment effects between CGS+BT and CGS groups, the dummy variable will be coded 1 for CGS+BT and 0 for CGS. A significant coefficient of the dummy variable will indicate that the change rate of HbA_{1c} over time is different for the two groups due to the treatment effect. A similar strategy will be applied to evaluate the difference in the change of HbA_{1c} between CGS+BT and SC, and CGS and SC groups. Since Kovatchev's measures of glycemic variability and the proportion of CGS values in the normal range are on continuous scales that are comparable across repeated measures, these variables are also appropriate to use as outcome variables with IGM estimated using SAS Proc Mixed.

If the treatment groups are significantly different in the outcome measures, it is of interest to examine whether the difference in treatment groups persists after adjusting the covariates that are known to be associated with the outcome. This process will be conducted by including covariates in the IGM framework. For example, demographic variables (SES, parent marital status, etc.) and disease variables (diabetes onset age, duration, etc.) can be included in the models as covariates to improve the precision of estimation when evaluating the treatment effect. If the dummy variable is still significant with the covariates in the model, the interpretation is that the treatment accounts for some unique variance in the change of the outcome over time above and beyond the effects of the covariates. The effect of site difference will be included as a between-subject covariate with a random effect. Specific programming to include the site difference as a random effect using SAS Proc Mixed will follow Dmitrienko et al for clinical trial data collected from multiple sites.¹⁶²

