The testing of moderators will be conducted within the IGM framework outlined above. Specifically, HbA_{1c} will be the outcome and Time will be measured in months in the level-1 model. A dummy variable indicating treatment groups will be the predictor in level-2 models. A product term of the proposed moderator and the dummy variable, together with the main effect of the moderator candidate, will be entered into the level-2 models. A significant coefficient of the product term indicates that the candidate is a significant moderator. The analysis process will be carried out using Socioeconomic Status, Family composition, adolescent age at baseline, and scores on the Diabetes Problem Solving Interview, Parent-Adolescent Relationship Questionnaire, Diabetes Family Responsibility Questionnaire, Wiebe Parental Supportive Involvement Interview, and Diabetes Responsibility and Conflict Scale separately to determine significant moderators.

To interpret the effects of any significant moderators, estimated individual growth factors (e.g., the slope in linear trajectory) will be compared among subgroups of the moderator. The analysis will reveal subgroup differences in the change of outcome due to the treatment effects. For moderators measured on continuous scales, such as adolescent age at baseline, appropriate categorization will be applied for meaningful interpretation of the findings. Important covariates will be included in the models to adjust the possible effects

[figure not shown]
of the covariates. Within this model, site differences will be treated as a between-subject covariate to adjust for its possible effects on the outcome.

Hypothesis 3b: Improvements in HbA_{1c} during the 9-month Randomized Phase will be mediated by improved scores on the Diabetes Self-Management Profile, Diabetes Responsibility and Conflict Scale, Wiebe Parental Supportive Involvement Interview, Diabetes Problem Solving Interview, and Blood Glucose Monitoring Communication Questionnaire.

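### The HbA1c randomization stratum is in no analysis model, and the plan does not say where its three-level random center effect enters: make both prespecified fixed effects with time interactions

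*Combined protocol and SAP*

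**What the plan says.** **Randomization.** Section 5.3 says that "randomization will be stratified by two HbA_{1C} levels", with the cut at 8.8%, and that "randomization lists will be used for each center and HbA_{1c} stratum". Section 5.8 repeats both factors. Three centers and two strata make six cells.

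**Center in the analysis.** For Hypothesis 1, section 5.12 says "The effect of site difference will be included as a between-subject covariate with a random effect" and refers the coding to a cited SAS text. Hypothesis 2 also has site as a random effect. For Hypothesis 3a, "site differences will be treated as a between-subject covariate", with no mention of a random effect.

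**HbA1c stratum in the analysis.** Section 5.12 does not name it. The covariates given as examples for Hypothesis 1 are socioeconomic status, marital status, age at onset and duration. They may be added once the groups have been found to differ significantly. Section 5.9 provides adjustment for significant baseline differences. The Hypothesis 2 text says that important covariates will be included for all outcomes, without listing them.

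**Tested parameter.** Section 5.12 defines an intercept equation and a slope equation at level 2 and takes the treatment coefficient in the slope equation (β11) as the main interest.

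**Moderators.** The Hypothesis 3a list in section 5.10 begins "Socioeconomic status; Family composition; Adolescent age; Diabetes Problem Solving Interview, Parent-Adolescent Relationship Questionnaire; Diabetes Family Responsibility Questionnaire" and goes on to the parental involvement interview and the conflict scale. Baseline HbA1c is not on it.

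**The concern.** A factor that restricts the randomization should also be in the model. Stratifying makes the arms more alike than simple randomization would. If the model ignores the factor, the standard error still counts the variation that the design has removed, so the test is conservative and some of the precision is lost. Here one factor is missing by name, and it could come in only through generic covariate wording or after a significance result. The other factor is present but not fully specified. An intercept term for center and a slope term for center are different models, and only the second can adjust a slope test for centers whose trends differ.

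The gap also touches Aim 3. Section 4.2 reports, for sensor use, falls in HbA1c "with larger decreases among patients with higher baseline". Section 4.4 says of the family therapy trial: "The revised intervention exerted substantially greater effects on adherence and glycemic control, particularly among youths with" HbA1c above 9.0%. The plan's own background thus points to baseline HbA1c as a possible effect modifier.

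**Working it through.** **1. The plan's power figure.** Section 5.13 gives 94.5% for CGS+BT against CGS. Its inputs are a 0.8% difference at 12 months, SD 1.2% at baseline and 1.5% at the end, 50 per group, and visits at 0, 3, 6, 9 and 12 months. It does not state the significance level (two-sided 0.05 assumed here) or the variance components.

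With a linear growth model and no intercept-slope covariance (assumed):
- slope variance: τ = (1.5² − 1.2²)/144 = 0.81/144
- sum of squared visit times about their mean: 36 + 9 + 0 + 9 + 36 = 90
- variance of one youth's fitted 12-month change: V = 144(τ + σ²/90) = 0.81 + 1.6σ²
- SE of the group difference = √(2V/50); power = Φ(0.8/SE − 1.96)

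If residual error is 20% of baseline variance, σ² = 0.2 × 1.44 = 0.288, V = 1.271, SE = 0.2255 and power is 94.4%. Shares from 0.1 to 0.7 give 97.5% down to 72.9%. The stated figure is attainable but cannot be confirmed. The steps below use a share of 0.3 (assumed): σ² = 0.432, V = 1.501, SE = 0.2450, power 90.4%.

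**2. Does the placement of center and stratum matter?** One simulated data set was fitted (100 youths, complete visits, center and stratum differences in trend built in).

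| Center and stratum enter | Treatment-by-time coefficient | SE |
|---|---|---|
| not at all | −0.09306 | 0.01826 |
| intercept only | −0.09306 | 0.01826 |
| intercept and slope | −0.09504 | 0.01747 |

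Intercept terms left the tested coefficient unchanged. Slope terms reduced its SE by about 4% (0.01747/0.01826 = 0.957).

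**3. Size of the loss.** Hold V at 1.501 and let part of it come from the strata and centers. A stratum difference g in 12-month change (strata of equal size) contributes (g/2)², and a center SD s contributes s². At the top of the assumed range, g = 0.8% and s = 0.3%:
- variance within cells: W = 1.501 − 0.16 − 0.09 = 1.251
- true SE under stratified randomization = √(2 × 1.251/50) = 0.2237
- the unadjusted model reports 0.2450, so type I error = 2Φ(−1.96 × 0.2450/0.2237) = 0.032
- unadjusted power = Φ((0.8 − 1.96 × 0.2450)/0.2237) = 92.4%
- adjusted power = Φ(0.8/0.2237 − 1.96) = 94.7%

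Simulation of person-level slopes, blocked within the six cells (4,000 runs per setting, t tests), agrees:

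| g, s | Type I, unadjusted | Type I, adjusted | Power, unadjusted | Power, adjusted |
|---|---|---|---|---|
| 0, 0 | 0.048 | 0.049 | 89.5% | 89.6% |
| 0.5, 0 | 0.049 | 0.051 | 89.9% | 90.6% |
| 0.8, 0 | 0.038 | 0.049 | 90.6% | 92.6% |
| 0.8, 0.3 | 0.035 | 0.052 | 91.8% | 94.1% |

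The largest gain is 94.1 − 91.8 = 2.3 points. The mean estimate was the same with and without adjustment in every setting.

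**4. Three centers as a random effect.** With 2 degrees of freedom, a 95% interval for a between-center variance runs from 2/7.378 = 0.27 to 2/0.0506 = 39.5 times the estimate.

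**5. Baseline HbA1c as a moderator.** With 25 youths per stratum-by-arm cell, the SE of the interaction is √(4V/25). For residual shares of 0.2 to 0.4, V is 1.271 to 1.732 and the SE is 0.451 to 0.526. Power is about 12% to 14% for an interaction of 0.4% and 33% to 43% for 0.8%.

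**The case against.** The strongest reply is that much of this is already covered.

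- **Center is in the models** for Hypotheses 1, 2 and 3a. A reader might infer that neither stratification factor reaches the analysis. That is wrong for center.
- **Level 2 includes the slope equation.** Section 5.12 places between-subject variables in the level-2 models. A reader might infer that center cannot adjust the tested slope, but nothing confines it to the intercept. Only the lack of a stated placement stands.
- **No treatment-by-center term is proposed.** A reader might fear a slope test on 2 degrees of freedom with a severe loss of power. The plan does not specify such a term, so that loss cannot be charged to it.
- **The center effect may be negligible.** Section 1 says that earlier sensor trials found no significant site effects on primary outcomes. A reader might add that a three-level random effect will often be estimated as zero. That happens most often when there is no center effect to adjust for, so it shows little harm.
- **Baseline HbA1c is the first value of the outcome**, which partly makes up for omitting the stratum when the outcome is HbA1c. It does not do so for the behavioral outcomes of Hypothesis 2, or for strata with different trends.
- **The generic clause on important covariates could reach the stratum.** It could, but it names nothing, and a design factor should not depend on a later choice.
- **The moderator evidence is thin.** The sensor pilots in section 4.2 had no control arm, so larger falls from a higher baseline may be regression to the mean. Aim 3 is framed around demographic variables and behaviors. The family therapy trial is the better support. This justifies an exploratory estimate and no more.

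**Conclusion.** The point holds in a modest form. The HbA1c stratum is missing by name from every analysis model. Center is included, but as a three-level random effect for Hypotheses 1 and 2 with no stated placement. A fixed effect is the better choice with three centers.

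The unadjusted estimate is not biased. The loss is a slightly conservative test and at most about 2.3 points of power. That bound rests on assumptions that the documents do not supply: residual error at 30% of baseline variance, zero intercept-slope covariance, two-sided 0.05, equal strata, stratum trends up to 0.8% apart over 12 months, and a center SD of trend up to 0.3%. If strata and centers share the same trend, the gain is essentially nil. The change is worth making because it costs almost nothing and settles the model before the data are seen.

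**What to change.** In section 5.12, for the primary Hypothesis 1 and 2 models and for the Hypothesis 3 models:

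- Enter center (2 df) and HbA1c stratum as used for randomization (1 df) as fixed effects, each with its interaction with time. Do this whatever the baseline comparison or the treatment test shows.
- Remove the random center term and use the same specification for every hypothesis.
- Keep the other covariates as a separate, supportive analysis.
- Optionally, add baseline HbA1c to Hypothesis 3a as an exploratory moderator, reported as an estimate with a confidence interval. A non-significant interaction should not be read as absence of moderation.

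The cost is a change of wording and 3 + 3 = 6 degrees of freedom among 150 youths. If the quadratic trajectory is chosen, the interactions with squared time add 3, for 9. No new data are needed.
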